4.3 Subject Recruitment, Enrollment and Screening

A maximum total of 17 subjects will be recruited from patients from the Mayo Clinic HIV Clinic and the Hennepin County Medical Center (HCMC). Potential study subjects will be identified and screened for inclusion and exclusion criteria by a member of the study team. Furthermore, other treating clinicians, including residents, fellows and staff physicians, in the Mayo Clinic HIV clinic and HCMC continuity clinic may refer potential study subjects to a study team member. Evaluation and documentation of inclusion and exclusion criteria will be obtained and recorded by an investigator prior to enrollment. Informed consent will be obtained by an MD investigator. Patients will be remunerated for participation in the study (see section 12.3).

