5.3 Method for Assigning Subjects to Treatment Groups

Each group (or dose level) will enroll and after 4 weeks of follow up of 3 patients treated with ixazomib at a particular dose will be reviewed for safety by DSMB before initiating enrollment into the next group (or dose level). All patients in the current cohort must have completed 4 weeks and the cohort's data reviewed by the by the Safety Monitoring Committee before patients in the next cohort can receive drug. Patients from the next cohort may complete the first two visits prior to DSMB review of earlier cohorts.

Dose limiting toxicities are defined in Section 6.17 Table 2. After all the subjects in each dosing group has completed Cycle 1 of ixazomib, the DSMB may recommend:

- (i) Proceed to next dose level, or
- (ii) Terminate trial, or
- (iii) Enroll a replacement subject for a withdrawn subject, or
- (iv) Add 5 more patients at previous dose group (maximum tolerated dose). The maximum tolerated dose is that level where no more than 0 out of 3 patients experience dose limiting toxicity.

If no DLT are observed in 3 subjects, the next dosing level will be initiated.

After DSMB review of the 4 mg dosing level, if no DLT are observed, the DSMB may recommend:

- (i) Terminating the trial
- (ii) Enroll 5 more patients at the maximum tolerated dose.

The NNRTIs etravirine and efavirenz are moderate CYP3A enzyme inducers and have potential to decrease systemic exposure to ixazomib. That possibility will be explored by measuring trough ixazomib levels in all patients and comparing ixazomib concentrations in patients on different ART regimens. The DSMB will have to consider the number of patients treated with NNRTIs in a particular group as the safety profile of a group may be underestimated if the majority of patients are treated with NNRTIs as part of their ARV regimen.

Additional data review by the DSMB will occur after Day 84 for each dosing cohort. At this time, the DSMB may recommend:

[figure not shown]
- (i) Proceed to uninterrupted weekly dosing on days 1, 8, 15 and 22 of a 28 day cycle, or
- (ii) Continue previous dosing on days 1, 8, and 15 of a 28 day cycle, or
- (iii) Enroll a replacement subject for a withdrawn subject, or
- (iv) Terminate dosing.

This determination will be made on an individual participant basis, and not a dosing cohort basis, and will be made based on the presence or absence of adverse drug effects that do not meet the definition of dose related toxicities.

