7.2 Statistical Methods

Descriptive Statistics

Univariate descriptive statistics and frequency distributions will be calculated, as appropriate for all variables. Baseline values for demographic, clinical, and outcome variables will be tabulated for the treatment groups. These analyses will help identify potential confounding variables to be used as covariates in sensitivity analyses. Putative prognostic variables that will be investigated through these descriptive analyses include variables such as age, sex, race/ethnicity, and duration of HIV infection, baseline CD4 T cell count and HIV viral load, mode of transmission, duration of ART, and duration of viral suppression.

Multiplicity

No *a priori* correction to the type I error rate is warranted for this study.

Primary Analysis

Ixazomib will be safe and well tolerated in HIV positive persons on suppressive ART.

Description statistics will be used to describe the rates of adverse effects by CTC grade of ixazomib among the dosing groups.

Secondary Analysis 1:

Ixazomib will reduce HIV DNA and replication competent viral reservoir size and improve CD4 T cell counts in HIV positive patients on suppressive ART.

To test this hypothesis, a mixed model will be estimated for each outcome separately. This model will consider linear trajectories and more flexible distribution of outcomes over time using each assessment point as a factor (i.e., a “repeated measures ANOVA formulation”). Given the limitations of the sample size, random effects for only subject (random intercept) models will be considered. These models will examine the treatment by time interaction and the linear trajectory model will be expected to have greater, but relatively poor, power to detect differences in outcomes such as viral load over time. An alpha of 0.1 or lower will be considered sufficiently significant to serve as preliminary evidence of a biologic effect to warrant further studies.

In the event the models are not able to be estimated from the data available, a planned post-hoc analysis will compare changes in secondary endpoints between participants on integrase inhibitor-based ART and non-nucleoside reverse transcriptase-based ART.

Interim Analysis

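### If a secondary outcome's mixed model cannot be fitted, the planned fallback compares ART classes and so does not test change on ixazomib for that outcome

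*Combined protocol and SAP*

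**What the plan says.** Section 7.2, Secondary Analysis 1, states the hypothesis: "Ixazomib will reduce HIV DNA and replication competent viral reservoir size and improve CD4 T cell counts in HIV positive patients on suppressive ART". The test is named next: "To test this hypothesis, a mixed model will be estimated for each outcome separately". The models use a random intercept only, and the section sets this threshold: "An alpha of 0.1 or lower will be considered sufficiently significant to serve as preliminary evidence of a biologic effect". It also says "No *a priori* correction to the type I error rate is warranted for this study".

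The contingency follows: "In the event the models are not able to be estimated from the data available", then "a planned post-hoc analysis will compare changes in secondary endpoints between participants on integrase inhibitor-based ART and non-nucleoside reverse transcriptase-based ART". No test, threshold or covariates are given for this comparison. I found no paired or nonparametric test of change from baseline anywhere in the document. Section 7.2 does plan descriptive statistics for all variables.

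The design facts that matter are these:

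- The Study Summary describes an open-label dose escalation with no reference therapy. Section 4.3 says "A maximum total of 17 subjects will be recruited from patients".
- Section 5.2 keeps each participant on the existing ART regimen. Section 4.1 asks for at least three active drugs and sets no quota by class.
- Section 6 obtains the digital PCR and outgrowth measurements from two leukapheresis samples, one at baseline and one after treatment.
- Section 1.1 describes outgrowth assays as infrequently positive in ART-suppressed patients.
- Section 5.3 gives a possible reason for looking at ART class: "The NNRTIs etravirine and efavirenz are moderate CYP3A enzyme inducers and have potential to decrease systemic exposure to ixazomib".

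**The concern.** The hypothesis is about change on ixazomib. The fallback asks whether that change differs between two groups of participants who all received ixazomib and who differ in background ART. A reduction common to both groups cancels out of the comparison. A null result would therefore say nothing about whether ixazomib works, and a positive result would show only that the classes differ, for whatever reason.

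The outcome most exposed is culturable HIV, the replication-competent reservoir measure. With two values per person and many negatives expected, its model is the one most likely to fail. For that outcome the plan would then offer no inferential test of its own hypothesis, although the paired samples needed for one would be in hand.

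**Working it through.** **Inputs from the documents.** Maximum sample: four groups of 3 plus one of 5, so 4 × 3 + 5 = 17, matching Section 4.3. Alpha is 0.1 (Section 7.2); sidedness is not stated, so I take it as two-sided and carry it over to the fallback, which has no threshold of its own. Section 1.1 reports a geometric mean fall of 37% in HIV DNA with ixazomib alone ex vivo (11 patients, P = 0.02). The plan gives no power figure for the secondary endpoints (Section 7.1 bases the size on recruitment), so there is nothing to reproduce.

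**What the fallback estimates.** Let μ_I and μ_N be the mean log10 changes in integrase-inhibitor and NNRTI users. The contrast estimates μ_N − μ_I. If ixazomib produces the same change δ in both, then μ_N − μ_I = δ − δ = 0 for every δ, and the rejection rate equals alpha. A simulation of 40,000 runs (5 NNRTI and 12 integrase-inhibitor users, assumed SD of change 0.25 log10) gave:

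| True common fall | Class contrast rejects | Paired test rejects |
|---|---|---|
| 0% | 10.0% | 10.1% |
| 37% | 9.8% | 93.6% |
| 90% | 10.1% | 100% |

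**An illustrative SD for HIV DNA.** log10(1 − 0.37) = −0.201. If the P-value came from a paired t-test on log10 values (an assumption, as the test is not named), then t on 10 df at two-sided P = 0.02 is 2.764, and SD = 0.201 × √11 / 2.764 = 0.241. In-vivo variation over months may well be larger, so I use 1, 1.5 and 2 times this value.

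**Power of a within-person test.** Noncentrality is 0.201 / (SD/√n), with a two-sided t-test at alpha 0.1. At n = 17 and SD 0.241 this is 0.201 / (0.241/√17) = 3.44 against a critical value of 1.746.

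| SD (log10) | n = 17 | n = 12 |
|---|---|---|
| 0.24 | 95% | 85% |
| 0.36 | 71% | 56% |
| 0.48 | 50% | 39% |

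Under the same uniform effect, the class contrast stays at 10% in every cell.

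**When the effect does differ by class.** Take n = 17, SD 0.241 and standard error SD × √(1/k + 1/(17 − k)) for k NNRTI users. If NNRTI users have half the log effect (difference 0.100), power is 17%, 19% and 21% for k = 3, 5 and 8. If they have no effect at all (difference 0.201), it runs from 35% (k = 3) to 50% (k = 8). These figures assume everyone is on one of the two classes.

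**The outgrowth outcome.** The calculations above concern a continuous measure. For positive/negative pairs, an exact sign (McNemar) test uses only discordant pairs. The smallest two-sided P with d discordant pairs is 2 × 0.5^d, which is 0.125 for d = 4 and 0.0625 for d = 5. At least 5 discordant pairs are needed for P < 0.10, and with 5 all must go the same way. If few baseline samples are positive, that may not be attainable.

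**The case against.** Several points can be made for the plan, and most of them limit the concern.

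- The models are fitted outcome by outcome. CD4 count and clinical proviral DNA are measured at many visits (Section 6.16, Table 1), and digital PCR is continuous with two samples. A random-intercept model is ordinarily estimable for these. A reader might infer that the trial as a whole would have no test of its secondary hypothesis. The documents do not support that: failure for one outcome leaves the others tested, and descriptive statistics remain for the one that failed.
- The class comparison has a possible rationale. If some NNRTIs lower ixazomib exposure, it is a weak exposure-response proxy. That stands, but Section 7.2 does not say so. The protocol names only efavirenz and etravirine as inducers, while the fallback pools all NNRTI regimens and leaves out participants on neither class. ART class is not randomised either.
- A reader might infer that ART class is in fact unbalanced across the dose groups, or that the plan rules out dose adjustment. No class distribution is given and no method for the fallback is stated. Confounding with dose is possible in groups of three, not established.
- A reader might also infer that a class difference would be reported as the reservoir result. The plan calls the analysis post-hoc and attaches the 0.1 criterion to the mixed models, so this is speculation.
- The power contrast is for HIV DNA, where the fallback is least likely to be used. It rests on a 96-hour ex vivo experiment. A uniform 37% fall across 1 to 4 mg is generous: Section 1.5 expects under 30% proteasome inhibition at 1 mg, and 8 of 12 patients' cells responded in a related experiment in Section 1.1. Seventeen is a maximum before withdrawals. All of this is fair, and the figures are illustrative.
- This is a contingency for a secondary analysis in a pilot whose primary analysis is descriptive safety. That bears on priority, not on whether the fallback answers its question.

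**Conclusion.** The concern holds for any secondary outcome whose mixed model cannot be estimated, most plausibly viral outgrowth. For that outcome the only inferential replacement does not estimate change on ixazomib, and its part of the hypothesis would be left with descriptive statistics. This conclusion follows from the design and needs no assumption about variance.

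The size is illustrative and applies to HIV DNA. With a uniform 37% fall, two-sided alpha 0.1 and SD of change 0.24 to 0.48 log10, within-person power is about 95% to 50% at n = 17 and 85% to 39% at n = 12, against 10% for the class contrast. The effect and SD are assumptions drawn from ex vivo data, with the SD widened. No power is claimed for outgrowth, where the proposed exact test may itself have little. The point deserves correction before analysis, but it concerns a conditional, secondary analysis and does not touch the primary safety assessment.

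**What to change.** Replace the contingency sentence in Section 7.2 with wording to this effect:

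- If an outcome's model cannot be estimated, test within-person change from baseline in all treated participants with paired samples.
- For continuous outcomes, use an exact Wilcoxon signed-rank or sign-flip permutation test on the log10 change, with a 90% confidence interval and a stated rule for values below detection.
- For outgrowth positivity, use an exact sign (McNemar) test. State that it needs at least 5 discordant pairs, all in one direction when there are only 5, to reach two-sided P < 0.10, and so may have little power.
- State that a before-after comparison is uncontrolled, so a change cannot be attributed to ixazomib on this evidence alone.
- Keep the ART-class comparison as a labelled exploratory analysis, grouped as efavirenz or etravirine versus other regimens, with dose taken into account where numbers allow.

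The cost is a few sentences in Section 7.2. No new samples, visits or assays are needed.

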7.3 Subject Population(s) for Analysis

The per-protocol analysis set will be of participants followed according to the study schedule. This subset of the entire study sample will be of particular interest to the mechanistic studies since all data will be available. The results of this potentially non-representative subset will be compared to the results obtained using the Safety Evaluable Analysis Set as a sensitivity analysis. Should the results disagree qualitatively, the ITT results will be considered the less-biased results; however, a careful examination of putative causes for the differences will be fully investigated to inform a Phase II/III confirmatory study.

The Safety Evaluable Analysis Set will consist of all participants that have at least one dose of study medication. This analysis set will serve as the basis for the primary analysis noted above and adverse event reporting of treatment emergent and/or worsening events.

8 Safety and Adverse Events

8.1 Definitions

Unanticipated Problems Involving Risk to Subjects or Others (UPIRTSO)

Any unanticipated problem or adverse event that meets the following three criteria:

- **Serious:** Serious problems or events that results in significant harm, (which may be physical, psychological, financial, social, economic, or legal) or increased risk for the subject or others (including individuals who are not research subjects). These include: (1)

death; (2) life threatening adverse experience; (3) hospitalization - inpatient, new, or prolonged; (4) disability/incapacity - persistent or significant; (5) birth defect/anomaly; (6) breach of confidentiality and (7) other problems, events, or new information (i.e. publications, DSMB reports, interim findings, product labeling change) that in the opinion of the local investigator may adversely affect the rights, safety, or welfare of the subjects or others, or substantially compromise the research data, **AND**

- **Unanticipated:** (i.e. unexpected) problems or events are those that are not already described as potential risks in the protocol, consent document, not listed in the Investigator's Brochure, or not part of an underlying disease. A problem or event is "unanticipated" when it was unforeseeable at the time of its occurrence. A problem or event is "unanticipated" when it occurs at an increased frequency or at an increased severity than expected, **AND**
- **Related:** A problem or event is "related" if it is possibly related to the research procedures.

Adverse Event

An untoward or undesirable experience associated with the use of a medical product (i.e. drug, device, biologic) in a patient or research subject. An AE can therefore be any unfavorable and unintended sign (including an abnormal laboratory finding), symptom, or disease temporally associated with the use of a medicinal (investigational) product whether or not it is related to the medicinal product. This includes any newly occurring event, or a previous condition that has increased in severity or frequency since the administration of ixazomib.

An abnormal laboratory value will not be assessed as an AE unless that value leads to discontinuation or delay in treatment, dose modification, therapeutic intervention, or is considered by the investigator to be a clinically significant change from baseline.

Serious Adverse Event

Adverse events are classified as serious or non-serious. Serious problems/events can be well defined and include;

- death
- life threatening adverse experience
- hospitalization
- inpatient, new, or prolonged; disability/incapacity
- persistent or significant birth defect/anomaly

and/or per protocol may be problems/events that in the opinion of the sponsor-investigator may have adversely affected the rights, safety, or welfare of the subjects or others, or substantially compromised the research data.

All adverse events that do not meet any of the criteria for serious, should be regarded as **non-serious adverse events**.

Adverse Event Reporting Period

For this study, the study treatment follow-up period is defined as 30 days following the last administration of study treatment.

Preexisting Condition

A preexisting condition is one that is present at the start of the study. A preexisting condition should be recorded as an adverse event if the frequency, intensity, or the character of the condition worsens during the study period.

General Physical Examination Findings

At screening, any clinically significant abnormality should be recorded as a preexisting condition. At the end of the study, any new clinically significant findings/abnormalities that meet the definition of an adverse event must also be recorded and documented as an adverse event.

Post-study Adverse Event

All unresolved adverse events should be followed by the sponsor-investigator until the events are resolved, the subject is lost to follow-up, or the adverse event is otherwise explained. At the last scheduled visit, the sponsor-investigator should instruct each subject to report, to the sponsor-investigator, any subsequent event(s) that the subject, or the subject's personal physician, believes might reasonably be related to participation in this study.

Table 3. Adverse Events to be Graded at Each Evaluation

SYSTEM ORGAN CLASS	Adverse event/Symptoms	Baseline	Each evaluation
Investigations	Creatinine increased	X	X
	Neutrophil count decreased	X	X
	Platelet count decreased	X	X
General disorders and administration site conditions	Edema limbs	X	X
	Fatigue	X	X
Gastrointestinal Disorders	Nausea	X	X
	Vomiting	X	X
	# of Stools	X	
	Diarrhea		X
	Constipation		X
Infections and infestations	Sepsis	X	X
Blood and lymphatic system disorders	Febrile neutropenia	X	X
Skin and subcutaneous tissue disorders	Rash, maculopapular	X	X
Nervous system	Peripheral sensory neuropathy	X	X

disorders	Peripheral motor neuropathy	X	X
	Cognitive disturbance	X	X

Hospitalization, Prolonged Hospitalization or Surgery

Any adverse event that results in hospitalization or prolonged hospitalization should be documented and reported as a serious adverse event unless specifically instructed otherwise in this protocol. Any condition responsible for surgery should be documented as an adverse event if the condition meets the criteria for an adverse event.

Neither the condition, hospitalization, prolonged hospitalization, nor surgery are reported as an adverse event in the following circumstances:

- Hospitalization or prolonged hospitalization for diagnostic or elective surgical procedures for a preexisting condition. Surgery should **not** be reported as an outcome of an adverse event if the purpose of the surgery was elective or diagnostic and the outcome was uneventful.
- Hospitalization or prolonged hospitalization required to allow efficacy measurement for the study.
- Hospitalization or prolonged hospitalization for therapy of the target disease of the study, unless it is a worsening or increase in frequency of hospital admissions as judged by the clinical investigator.

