3.2 Primary Study Endpoints

The primary endpoint to be analyzed in the study is the safety and tolerability of ixazomib in HIV positive patients on antiretroviral therapy.

(See pages 39 and 49 for a list of adverse events to be assessed).

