Screening for peripheral neuropathy will occur at baseline (for study exclusion), and at each study visit (for safety monitoring), by administration of the European Organization for Research and Treatment of Cancer QLQ-CIPN20 Questionnaire. The 20-item CIPN-specific questionnaire which includes three scales assessing sensory (9 items), motor (8 items), and autonomic (3 items) symptoms and functioning with each item formatted the same as items of the EORTC QLQ-C30. It was developed to be used in conjunction with the EORTC QLQ-C30 following the EORTC guidelines for module development (15911236). The EORTC QLQ-CIPN20 has been tested in cancer patients receiving a variety of chemotherapies and has been shown to have internal consistency reliability based on Cronbach's alpha coefficients of 0.82, 0.73, and 0.76 for the three scales, respectively (PMID 23543373). The questions that comprise the QLQ-CIPN20 are listed in Appendix II. Any affirmative answer to questions in the QLQ-CIPN20 will trigger a further clinical assessment, and grading of suspected peripheral neuropathy according to the (CTCAE) Version 4.0 scale (Appendix I). Further clinical assessment of suspected peripheral neuropathy will be referred to a qualified physician in the area of drug-induced peripheral neuropathy.

The following toxicities will be considered to be dose limiting toxicities:

- Any \geq Grade 4 toxicity
- Any Grade 3 AE (except if there is clear evidence that it is not ixazomib related – i.e. a plausible alternative reason).
- Any \geq Grade 1 peripheral neuropathy (PN)

Specific management of toxicities in individual participants is discussed below.

Study related biology assays for the secondary outcomes include:

- CD4 T cell count, CD8 T cell count and CD4/CD8 ratio – by routine clinical flow cytometry (Mayo Medical Labs).
- Plasma HIV RNA viral load – by routine clinical RT-qPCR (Mayo Medical Labs).
- HIV Proviral DNA – by clinical qPCR (Mayo Medical Labs)
- Cell associated HIV DNA by digital droplet PCR – Peripheral blood CD4 T cells will be isolated from baseline and post-treatment leukapheresis samples by magnetic bead negative selection. Cell associated HIV DNA will be quantified by digital droplet PCR using RainDance™ ddPCR system ([name] HIV Laboratory).

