8.2 Recording of Adverse Events

At each contact with the subject, the study team must seek information on adverse events by specific questioning and, as appropriate, by examination. AEs may be spontaneously reported by the patient and/or in response to an open question from study personnel or revealed by observation, physical examination, or other diagnostic procedures. Any clinically relevant deterioration in laboratory assessments or other clinical finding is considered an AE. When possible, signs and symptoms indicating a common underlying pathology should be noted as one comprehensive event. For serious AEs, the investigator must determine both the intensity of the event and the relationship of the event to ixazomib administration.

Information on all adverse events should be recorded immediately in the source document, and also in the appropriate adverse event section of the case report form (CRF). All clearly related signs, symptoms, and abnormal diagnostic, laboratory or procedure results should be recorded in the source document.

All adverse events occurring during the study period must be recorded. The clinical course of each event should be followed until resolution, stabilization, or until it has been ultimately determined that the study treatment or participation is not the probable cause. Serious adverse events that are still ongoing at the end of the study period must be followed up, to determine the final outcome. Any serious adverse event that occurs after the study period and is considered to be at least possibly related to the study treatment or study participation should be recorded and reported immediately.

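### The primary safety rates are by CTC grade, but 8.1 leaves Grade 1 laboratory changes and lower-grade anaemia to investigator judgement, in conflict with Table 3

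*Combined protocol and SAP*

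**What the plan says.** Section 3.2 words the endpoint broadly: "The primary endpoint to be analyzed in the study is the safety and tolerability of ixazomib in HIV positive patients on antiretroviral therapy". The analysis in 7.2 is more specific: "Description statistics will be used to describe the rates of adverse effects by CTC grade of ixazomib among the dosing groups".

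Four places bear on whether a laboratory value becomes an adverse event.

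- The general definition in 8.1 covers "any unfavorable and unintended sign (including an abnormal laboratory finding", with no threshold of grade or action.
- The next paragraph of 8.1 narrows this: "An abnormal laboratory value will not be assessed as an AE unless that value leads to discontinuation or delay in treatment, dose modification". The sentence goes on to admit values that lead to therapeutic intervention, "or is considered by the investigator to be a clinically significant change from baseline".
- Section 8.2 has its own wording: "Any clinically relevant deterioration in laboratory assessments or other clinical finding is considered an AE".
- "Table 3. Adverse Events to be Graded at Each Evaluation" has three laboratory-count or chemistry rows (creatinine, neutrophils, platelets), marked at baseline and each evaluation. It has no row for haemoglobin, AST, ALT or bilirubin.

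One list of dose-limiting toxicities, in section 6 (Study Procedures), includes "Any Grade 3 AE (except if there is clear evidence that it is not ixazomib related". Section 5.3 places the DLT definitions in Table 2 (6.17), which has a similar Grade 3 row.

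**The concern.** A table of rates by CTC grade is interpretable only if the same rule decides for every patient and dose group which graded values are counted. Here a mild platelet fall must be graded under Table 3, yet under 8.1 it is not an adverse event unless someone acts on it or considers it significant. No text says which rule feeds the primary table. The investigators know the dose, and each escalation group has 3 patients, so a difference in one or two judgements can change what a dose level appears to show.

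Mild effects also feed a decision. Under 5.3, after Day 84 the DSMB decides patient by patient whether to move to uninterrupted weekly dosing, on the basis of adverse drug effects that fall short of dose-related toxicity. The laboratory part of that class of effects is what 8.1 leaves to judgement.

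**Working it through.** There is no sample size, power or alpha figure to reproduce: the primary analysis is descriptive and 7.1 rests the sample size on recruitment. The check sets the 8.1 rule beside Tables 2 and 3, test by test.

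| Test | Row in Table 3 | Own row in Table 2 | Consequence under 8.1 |
|---|---|---|---|
| Platelets, neutrophils | Yes | Grade 2: dose omitted; Grade 3 or higher: discontinued | Grade 2 or higher is an AE. Grade 1 only if treated or judged significant, although Table 3 grades it |
| AST, ALT, total bilirubin | No | Grade 2 or higher: dose omitted | Grade 2 or higher is an AE. Grade 1 only if treated or judged significant |
| Creatinine | Yes | None | Lower grades only if acted on or judged significant, although Table 3 grades them |
| Haemoglobin | No | None | Lower grades only if acted on or judged significant |
| Electrolytes | No | None | As for haemoglobin |

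**How wide the discretionary band is.** Section 4.1 requires platelets and neutrophils at or above the lower limit of normal at entry. Table 2 first acts below 75,000/mm³ for platelets and below 1500/mm³ for neutrophils. A fall from normal to just above those limits triggers nothing.

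**Grade 3 wording.** For tests with no Table 2 row, 8.1 makes a value an AE if it leads to discontinuation, while Table 2 discontinues for a Grade 3 AE. Each condition refers to the other. The loop is only partial, because treatment of the abnormality or a judgement of significance also makes it an AE.

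**Illustration for anaemia.** Section 1.4 reports anaemia in 21% of 201 patients in single-agent oral studies, any causality, with no split by grade. Suppose that rate applied here and that a share *f* of cases were counted (*f* is assumed; the documents do not give it).

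- Expected cases in 17 patients: 17 × 0.21 × *f*
- Chance of at least one in a group of 3: 1 − (1 − 0.21 × *f*)³

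| *f* | Expected in 17 | Chance of at least one in 3 |
|---|---|---|
| 1.00 | 3.57 | 1 − 0.79³ = 0.507 |
| 0.75 | 2.68 | 1 − 0.8425³ = 0.402 |
| 0.50 | 1.78 | 1 − 0.895³ = 0.283 |
| 0.25 | 0.89 | 1 − 0.9475³ = 0.149 |

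This shows only how sensitive a 3-patient group is to the counting rule. It is not an estimate of the loss.

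**The case against.** The strongest reply is that little is truly hidden. The 8.1 sentence lets the investigator admit a value of any grade. Table 3 already grades the two main cytopenias and creatinine. Table 2 makes Grade 2 or higher platelet, neutrophil and liver-test changes AEs automatically. Blood counts are taken at nearly every visit and chemistry on schedule. Under 9.4.1 the DSMB reviews laboratory safety data before the next group enrols, and its charter is to hold its own analysis plan. Section 7.2 promises descriptive statistics for all variables, as appropriate. The 8.2 wording is also close in substance to the judgement clause in 8.1.

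Most of this stands, and it rules out three stronger readings that a reader might infer.

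- *Low-grade laboratory toxicity is excluded by rule.* It is not; its capture is discretionary.
- *Grade 3 laboratory values can generally escape being DLTs.* For platelets, neutrophils and liver tests, Table 2 acts directly. The gap is confined to tests without a Table 2 row, and it also requires that a Grade 3 change goes untreated and is judged not significant.
- *Liver toxicity is a main expected risk that goes uncounted.* It is not among the nonclinical risks in 1.3, the frequent events in 1.4 or the reactions listed in 1.5. The case for adding liver tests to Table 3 is that Table 2 acts on them.

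The safeguards still do not settle the point. DSMB review of laboratory data does not define the primary rates, and the general sentence in 7.2 names no graded or shift table.

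**Conclusion.** The concern holds as an inconsistency with a limited consequence. Grade 1 platelet, neutrophil and liver-test changes, lower-grade creatinine changes and lower-grade anaemia enter the primary rates by investigator judgement unless they are treated or otherwise acted on. For platelets, neutrophils and creatinine this contradicts the threshold-free grading in Table 3. Anaemia is the clearest gap: it is a listed risk in 1.3 and 1.5 and has no row in Table 2 or Table 3.

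The number of patients affected cannot be derived. It is tempting to multiply the single-agent rates by the maximum enrolment (0.34 × 17 = 5.8 for thrombocytopenia, 0.21 × 17 = 3.6 for anaemia) and call these the patients at stake. The documents do not support that. The rates are events of any causality without a grade split, from an oncology programme. This trial requires normal platelets and haemoglobin of at least 12.0 g/dL at entry, and Grade 2 or higher thrombocytopenia is counted in any case. Nor do the documents show that under-counting would be worst at low doses.

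The conclusion assumes that 8.1 is applied as written and that no unpublished charter or analysis plan already specifies graded laboratory tables.

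**What to change.** 1. Reconcile 8.1 and 8.2 with Table 3, so that one rule states how laboratory values enter the primary safety analysis.
2. Add haemoglobin, AST, ALT and bilirubin to Table 3.
3. Derive CTCAE v4.0 grades by program from every scheduled blood count and chemistry value. Report worst post-baseline grade and shift from baseline by dose group in the Safety Evaluable Analysis Set, whether or not an AE was recorded, as part of the primary safety analysis. State which pre-dose value is the baseline.
4. Give the DSMB the same table at its reviews, including the Day 84 review.
5. The sponsor should reconcile the Grade 3 DLT wording across section 6, Table 2 and 8.1 for tests with no Table 2 row. This point proposes no change to any dose or management rule.

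The cost is one additional programmed table from data already collected under Table 1, plus wording changes. The reported laboratory toxicity rates are likely to look less favourable than they would under 8.1 as it stands.
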